3.7.3. Reporting procedures

For each SAE, the Investigator will complete a SAE Report Form in English and assess the relationship of each SAE to study treatment. The completed form(s) should be sent by e-mail to

the Sponsor within 24 hours of first knowledge of the SAE (as outlined in [Section 3.7.1](#) and [Section 3.7.2](#)). The initial SAE should be reported immediately, even if only preliminary information is available. Follow-up information should be sent by the same Investigator, restating the date of the original report. Either a new SAE form is sent (stating that it is a follow-up), or the original one is resent (with the new information highlighted and a new date provided). The follow-up should describe whether the event has resolved or continues, if and how it was treated, whether the blind was broken or not, and whether the patient continued or discontinued study participation. The form confirmation will be retained.

Pregnancy follow-up (as outlined in [Section 3.6.5](#)) should be reported to the IRB within 24 hours of first knowledge on a Pregnancy Report Form. Follow up will describe the outcome of the pregnancy, including any voluntary or spontaneous termination, details of the birth, and the presence or absence of any congenital abnormalities or birth defects.

3.8. Appropriateness of Safety Measurements

The safety assessments in the study are standard safety measures in clinical trials.

4. STATISTICAL METHODS

4.1. General Considerations for Data Analysis

The focus of the statistical analysis will be the comparison with controls of the photoallergic response to the study products. The diagnosis of photosensitization response will be made by the Investigator based on review of the observed skin responses after Challenge.

The mean score by subject and treatment, including all scores assigned during Induction, will be analyzed in the analysis of variance with factors subject and treatment. All pairwise treatment comparisons will be performed.

The statistical analyses described below will be supplemented by a comprehensive SAP which will be finalized before the database is locked. Any changes to the statistical plans will be described and justified in the final report.

All statistical processing will be performed using the SAS® system (version 9.2 or higher). No interim or subgroup analyses are planned.

4.2. Sample Size and Power Considerations

The sample size of 50 evaluable subjects conforms to industry and regulatory standards for determination of irritation/sensitization when topical application to skin is followed by light exposure.

4.3. Subject Populations for Analysis

All subjects who receive treatment will be evaluable for AEs. The analysis of local tolerability (photoirritation) will be based off all subjects who complete the Induction Phase of the study. Subjects who completed Induction are those who have received at least 6 applications/irradiation of study products, and at least 11 subsequent evaluations during Induction. The evaluation of photosensitization will be based on all subjects who complete the Challenge Phase of the study. Subjects who completed Challenge are those who have received at least 6 applications/irradiation of study products, and at least 11 subsequent evaluations during Induction, completed the Rest Phase and have received one application of study products at Challenge, subsequent irradiation and complete the 3 post-irradiation evaluations for that product.

4.3.1. Background and Demographic Characteristics

Descriptive statistics will be used to summarize demographic characteristics (age, gender, Fitzpatrick skin type, and race) and background characteristics for the randomized subject population. Past/coexistent medical history information for all randomized subjects will be presented in a by-subject listing.

4.3.2. Study Product/Visit Compliance

Descriptive statistics will be used to summarize study product compliance for the randomized subject population.

4.4. Prior and Concomitant Medications

Prior and concomitant medication information for all randomized subjects will be presented in a by-subject listing.

4.5. Efficacy Evaluation

This section is not applicable to this study.

4.6. Safety Evaluation

4.6.1. Assessment of Responses

All assigned scores during Induction and Challenge will be summarized by frequency counts by time point and treatment. The incidence of reactions will be summarized by frequency counts for each treatment. The mean score by subject and treatment, including all scores assigned during Induction, will be analyzed using Fisher's least significant differences in the analysis of variance (ANOVA) with factors subject and treatment. All pairwise comparisons will be performed: MC2-01 Cream on both the irradiated and non-irradiated sites, and MC2-01 Vehicle on both the irradiated and non-irradiated sites.

4.6.2. Photosensitivity

The determination of dermal photosensitization potential will be made by the Investigator based on specific scoring criteria derived from observations in the Challenge Phase of the study and confirmed in the Rechallenge Phase, if necessary. The incidence of photosensitization reactions will be summarized by frequency counts for each treatment. If photosensitization occurs, the 95% confidence interval for the proportion of subjects with photosensitization for each product will be calculated. Photosensitivity will not be determined by statistical methods.

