## **11.2 Subject Populations for Analysis**

Three analysis populations will be defined. All subjects who receive treatment will be evaluable for AEs (Population III). The evaluation of photosensitization will be based on all subjects who complete the challenge phase of the study (Population I). The analysis of local tolerability will be based off all subjects who complete the induction phase of the study (Population II).

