## **11.8 Safety Evaluation**

### **Assessment of Photosensitization Response**

The determination of dermal photosensitization potential will be based on specific scoring criteria derived from observations in the Challenge Phase of the study and confirmed in the Rechallenge Phase, if necessary. Criteria specified in the study protocol may cause the continuation of a subject into the Rechallenge Phase of the study. The diagnosis of a photosensitization response will be made by the Investigator based on review of the observed skin responses after Challenge. Photosensitivity will not be determined by statistical methods. All assigned scores during induction and challenge will be summarized by frequency counts by time point and treatment. The incidence of photosensitization reactions will be summarized by frequency counts for each treatment.

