## **12.CHANGES FROM THE PROTOCOL AND PLANNED ANALYSES**

There are no changes from the planned analyses in the protocol.

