## **15. OUTLINE OF PROPOSED TABLES, FIGURES, AND LISTINGS**

### **Summary Tables**

Table Number	Title
14.1.1	Summary of Subject Enrollment and Disposition
14.1.2	Summary of Subject Demographics and Baseline Characteristics
14.1.3	Summary of Study Product and Visit Compliance
14.2.1.1	Summary of Dermal Responses by Response Scores and Notations during Induction
14.2.1.2	Summary of Dermal Responses by Response Scores during Induction
14.2.1.3	Summary of Dermal Responses by Response Scores and Notations during Challenge
14.2.1.4	Summary of Dermal Responses by Response Scores during Challenge
14.3.1.1	Overall Summary of Adverse Events
14.3.1.2*	Summary of Treatment-Emergent Adverse Events by Maximum Severity
14.3.1.3*	Summary of Treatment-Emergent Adverse Events by Maximum Relationship

\*Tables 14.3.1.2 and 14.3.1.3 will only be included if there are a sufficient number of Treatment-Emergent AEs for multiple classified AE tables.

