**Statistical Analysis Plan**

**MC2 Therapeutics**  
Protocol No. MC2-01-C10

Page X of Y

Table 14.2.1.3: Summary of Dermal Responses by Response Scores and Notations During Challenge

Population I  
(N=XXX)

Time Post-Irradiation	MC2-01 cream		MC2-01 vehicle		Untreated
	Irradiated	Non-Irradiated	Irradiated	Non-Irradiated	Irradiated
N Sensitized [1]	xx (xx.x)	xx (xx.x)	xx (xx.x)	xx (xx.x)	xx (xx.x)
0 hours, n (%)					
-0	xx (xx.x)	xx (xx.x)	xx (xx.x)	xx (xx.x)	xx (xx.x)
[24 hours, n (%)] to [72 hours, n (%)]					
Response Score					
(Sum of Erythema and Edema)					
0	xx (xx.x)	xx (xx.x)	xx (xx.x)	xx (xx.x)	xx (xx.x)
1	xx (xx.x)	xx (xx.x)	xx (xx.x)	xx (xx.x)	xx (xx.x)
1 Hr	xx (xx.x)	xx (xx.x)	xx (xx.x)	xx (xx.x)	xx (xx.x)
2	xx (xx.x)	xx (xx.x)	xx (xx.x)	xx (xx.x)	xx (xx.x)
etc.	xx (xx.x)	xx (xx.x)	xx (xx.x)	xx (xx.x)	xx (xx.x)

[1] Sensitization classification made by the PI based on Challenge and Re-challenge

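### The 95% interval for photosensitization is planned only if a case occurs, with no method named and no place in the SAP, so a zero result would carry no upper bound

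*Protocol*

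**What the plan says.** Protocol 4.6.2 leaves the diagnosis to the Investigator and plans frequency counts per treatment. It then adds: "If photosensitization occurs, the 95% confidence interval for the proportion of subjects with photosensitization for each product will be calculated". Neither document names an interval method or says whether the interval is two-sided.

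Protocol 4.1 describes how the two documents relate: "The statistical analyses described below will be supplemented by a comprehensive SAP which will be finalized before the database is locked". SAP 11.8 carries over the counting sentence: "The incidence of photosensitization reactions will be summarized by frequency counts for each treatment". It does not carry over the interval sentence, and no confidence interval appears anywhere else in the SAP.

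The table list in SAP 15 has no output for an interval. There are two Challenge tables, 14.2.1.3 and 14.2.1.4, the second titled "Summary of Dermal Responses by Response Scores during Challenge". Both shells have an *N Sensitized* row, shown as n (%) and footnoted "Sensitization classification made by the PI based on Challenge and Re-challenge", and neither has an interval row. Listing 16.2.6.3 records only Yes or No for each site. SAP 12 nevertheless states: "There are no changes from the planned analyses in the protocol".

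On sample size, Protocol 4.2 says only this: "The sample size of 50 evaluable subjects conforms to industry and regulatory standards". SAP 11.9 argues in the same way. Neither gives an expected rate or a precision target.

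**The concern.** The primary objective is to determine photoallergic potential. Because the sample size rests on convention, the interval in Protocol 4.6.2 is the only planned statement of how precisely that question is answered. Its condition removes it when no case is seen, which is where a bare 0 (0.0) is most easily read as no risk.

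There are two gaps, and they act in different situations. The protocol's condition removes the interval when no case occurs on either product. The SAP's silence matters when a case does occur: the protocol then calls for an interval, but the programmer has no method and no table cell for it.

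**Working it through.** **Inputs.** Planned evaluable subjects: 50 (Protocol 4.2, SAP 11.9). Confidence level: 95% (Protocol 4.6.2). Two-sided limits and the values 45 and 55 for N are assumptions, the latter two to show a range. The figure of 50 cannot be reproduced, because the documents give no inputs for it.

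**Which outcomes give an interval under the plan as written**

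| Cases observed | Protocol 4.6.2 | Planned SAP output |
|---|---|---|
| None on either product | No interval | None |
| On one product only | Interval for that product; the wording can be read to include the other product too | None |
| On both products | Interval for both | None |

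**Denominator at a zero count.** SAP 11.2 bases photosensitization on Population I, and both Challenge shells are headed with it. SAP 11.2.1 adds to the completers only those non-completers who show photosensitization, and at a zero count there are none. Both SAP 11.2.1 and Protocol 4.3 define completion by product. SAP 11.2.1 asks for 10-17 days' rest, and Protocol 3.5.1 describes the Rest Period as approximately that long, so the two definitions agree for this purpose.

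**Exact (Clopper-Pearson) upper limit with zero cases:** 1 - 0.025^(1/N).

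- N = 50: 1 - 0.025^(1/50) = 7.11%
- N = 45: 7.87%
- N = 55: 6.49%

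**Chance of seeing no case in 50 at a true rate p:** (1 - p)^50.

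- p = 1%: 0.99^50 = 60.5%
- p = 2%: 0.98^50 = 36.4%
- p = 3%: 0.97^50 = 21.8%
- p = 5%: 0.95^50 = 7.7%

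Zero is therefore a likely result at true rates of 1% or 2%, and not a rare one at 3%.

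**Effect of the unnamed method.** The Wald interval is p ± 1.96 × sqrt(p(1 - p)/N).

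- 0/50: the standard error is 0, so Wald gives 0 to 0%, against 0 to 7.11% exact.
- 1/50: sqrt(0.02 × 0.98/50) = 0.0198, and 1.96 × 0.0198 = 0.0388, so Wald gives -1.88% to 5.88%. The exact limits, from beta quantiles, are 0.05% to 10.65%.

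**The case against.** The strongest reply is that the condition is a deliberate choice. Both documents say photosensitivity is not determined by statistical methods, no decision rule uses the interval, and anyone can compute the bound from N. All of that is true, and it limits the weight of the point. It does not justify the condition: an interval for one case is equally descriptive and equally computable, yet the protocol plans it.

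A second reply is that the SAP supplements the protocol and that SAP 15 is only an outline. It is not exhaustive: SAP 11.8 plans adverse events by system organ class and preferred term, and no listed table or shell shows that breakdown. This stands in part. The absent row does not prove that the interval was dropped, and the protocol interval may still apply once a case occurs. However, the SAP does flag its other event-driven outputs, the relocated-site and Rechallenge listings, and it never mentions the interval.

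Third, the Wald collapse at 0/50 cannot arise under the present plan when both products have no case, because no interval is then produced. That is correct. The collapse is a reason to name the method once the condition is removed.

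Fourth, *N Sensitized* might be read as including contact sensitization. Listing 16.2.6.3 puts the same footnote under a *Photosensitized* entry, so a single classification appears to be meant. A clear label on the new row is still sensible.

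**Conclusion.** The point holds and is minor. As planned, zero cases on both products would be reported without a bound, although 0/50 is compatible with a true rate of up to about 7% (exact, two-sided 95%; 6.5% to 7.9% for N from 55 down to 45). If a case does occur, the protocol interval has no method and no planned output, while SAP 12 declares no changes. No data are lost, and neither the Investigator's diagnosis nor any decision rule is affected. The figures assume an evaluable number close to the planned 50 and two-sided limits. The bound describes Population I, so it does not cover subjects excluded from it as pre-photosensitized during Induction.

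**What to change.** In SAP 11.8, state:

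> For MC2-01 cream and MC2-01 vehicle, the number and percentage of Population I subjects classified by the Investigator as photosensitized will be presented with the exact (Clopper-Pearson) two-sided 95% confidence interval at any count, including zero.

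Add an exact 95% CI row below *N Sensitized* in Tables 14.2.1.3 and 14.2.1.4, filled for the irradiated site of each product and labelled as referring to photosensitization. In SAP 12, record that the interval is now unconditional and exact. Optionally, if a photosensitized non-completer enters Population I, give the completers-only proportion as well.

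The cost is one sentence, one row in each of two shells and one SAP 12 entry, with no new data, visits or subjects. Protocol 4.1 also requires the change to be described and justified in the final report. It should be made before database lock, because SAP 9 requires written Sponsor approval, TKL management approval and archived documentation for later changes. The only downside is a zero result that reads slightly less favourably.

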4.6.3. Adverse Events

Adverse events will be summarized as an overall incidence of at least one event, incidence within body systems only, incidence by body system and preferred term, and by highest severity. Each subject will contribute only once (e.g., the first occurrence) to each of the rates, regardless of the number of occurrences (events) the subject experiences.

Treatment-emergent adverse events (TEAEs) will be summarized and tabulated by the system organ class and preferred term, by severity (mild, moderate, severe) and by relationship to study product (not related, possibly related, probably related, and definitely related).

Treatment-emergent will be defined as any AE with an onset date on or after the first study product administration date. Any event with a missing onset date will be included as a treatment-emergent AE.

Deaths and SAEs will be listed by subject.

4.7. Other topics

There are no other topics being evaluated.

4.8. Interim analyses

No interim analyses are anticipated.

4.9. Special Methods

This section is not applicable for this protocol.

5. ADMINISTRATIVE PROCEDURES

5.1. Ethics and Good Clinical Practice

This study must be carried out in compliance with the protocol and in accordance with TKL's SOPs. These are designed to ensure adherence to GCP guidelines, as described in:

- ICH Harmonized Tripartite Guidelines for GCP 1996. Directive 91/507/European Ethics Committee (EEC), The Rules Governing Medicinal Products in the European Community.
- United States (US) 21 Code of Federal Regulations (CFR) dealing with clinical studies (including parts 50 and 56 concerning informed consent and IRB/International Ethics Committee (IEC)/EEC regulations).
- Declaration of Helsinki, concerning medical research in humans (Recommendations Guiding Physicians in Biomedical Research Involving Human Subjects, Helsinki 1964 and amendments).

The PI agrees, when signing the protocol, to adhere to the instructions and procedures described in it and thereby to adhere to the principles of GCP that it conforms to.

5.2. Institutional Review Board

Before implementing this study, the protocol, the ICF and other information to subjects, must be reviewed by a properly constituted IRB. A signed and dated statement that the protocol and informed consent have been approved by the IRB must be given to Sponsor before study initiation. This committee must also approve any amendments to the protocol, other than administrative ones, and a signed and dated statement of approval must be sent to the Sponsor prior to initiation of the amendment procedures. The name and occupation of the chairman and the members of the IRB must also be supplied to Sponsor.

5.3. Informed consent

The Investigator or designee must explain to each subject the nature of the study, its purpose, the procedures involved, the expected duration, the potential risks and benefits involved, and any discomfort it may entail. Each subject must be informed that participation in the study is voluntary, that he/she may withdraw from the study at any time, and that withdrawal of consent will not affect his/her subsequent medical treatment or relationship with the treating physician.

This informed consent should be given by means of a standard written statement, written in non-technical language. The subject should read and consider the statement before signing and dating it, and he/she should be given a copy of the signed document. No subject can enter the study before informed consent has been obtained from him/her.

The ICF is considered to be part of the protocol and must be submitted by the PI with it for IRB approval. Any changes to the proposed ICF suggested by the PI must be agreed to by Sponsor before submission to the IRB and a copy of the approved version must be provided to Sponsor after IRB approval.

5.4. Declaration of Helsinki

The PI must conduct the study in accordance with the laws and regulations of the country in which the study is conducted, as outlined in the Declaration of Helsinki.

5.5. Changes in Planned Study Conduct

5.5.1. Protocol amendments

With the exception of changes in the visit schedule and/or administrative changes, any changes or additions to this clinical study protocol require a written protocol amendment that must be approved by Sponsor and the PI before implementation. Amendments significantly affecting the safety of subjects, the scope of the investigation or the scientific quality of the study, require additional approval by the appropriate IRB. A copy of the written approval of the IRB, which becomes part of the protocol, must be given to Sponsor. Examples of amendments requiring such approval are:

1. an increase in study product dosage or duration of product exposure of subjects,
2. a significant change in the study design (e.g., addition or deletion of a control group),
3. an increase in the number of invasive procedures to which subjects are exposed, and
4. addition or deletion of a test procedure for safety monitoring.

These requirements for approval should in no way prevent any immediate action from being taken by the Investigator or the Sponsor in the interests of preserving the safety of all subjects included in the study. If an immediate change to the protocol is felt to be necessary by the Investigator and is implemented by him/her for safety reasons the study Sponsor should be notified, and the IRB should be informed within 10 working days.

Amendments affecting only administrative aspects of the study do not require formal protocol amendments or IRB approval, but the IRB must be kept informed of such administrative changes. Examples of administrative changes not requiring formal protocol amendments and IRB approval that can be treated as administrative amendments include:

1. changes in the staff used to monitor studies, and
2. minor changes in the packaging or labeling of the study product.

5.5.2. Other changes in study conduct

Deviations from the planned study conduct are not permitted; any unforeseen changes in study conduct must be reported to the Sponsor and noted in the final clinical study report.

5.5.3. Termination or suspension of study

Both the Sponsor and the PI reserve the right to terminate or suspend the study at any time. If study termination is necessary, the procedures will be arranged on an individual study basis after review and consultation by both parties. It is the responsibility of the PI to notify the IRB of the

termination/suspension and the reason(s). In terminating the study, the Sponsor and the PI will ensure that adequate consideration is given to the protection of the subjects' interests.

5.6. Data handling and record keeping

5.6.1. Recording of data

Case report forms will be designed to identify each subject by subject entry number and, where appropriate, subject's initials, the product being evaluated, and the results observed. All entries to the CRFs must be made as instructed by the study Sponsor at study initiation. Data on subjects collected on CRFs during the study will be documented in an anonymous fashion, and the subject will only be identified by the subject number, and by his/her initials, if also required. If, as an exception, it is necessary for safety or regulatory reasons to identify the subject, both the study Sponsor and the PI are bound to keep this information confidential.

The PI must sign the designated page(s) of the CRFs, thereby stating that he/she takes responsibility for the accuracy of the data in the entire case record book. All records will be kept in conformance to applicable national laws and regulations.

The original signed ICF will be attached to each subject's file. When the study treatment is completed, the ICF will be kept in the appropriate file folder; otherwise a note indicating where the records can be located will be made.

